8. SAFETY EVALUATION

- 8.1. Frequency of Adverse Event Occurrence
- 8.1.1. Brief Summary of Adverse Events

Analysis Set: Safety Analysis Set Analysis Variables: Adverse Event

Category Classification:

Causal relationship with the investigational products [related, unrelated]
Severity [Mild, Moderate, Severe]

For the above analysis items, the following analyses of frequency distribution is performed.

- (1) All of the TEAEs
- (2) TEAEs Related to Investigational Drug
- (3) TEAEs by Severity
- (4) TEAEs Related to Investigational Drug by Severity
- (5) TEAEs leading to Discontinuation of Administration of Investigational Drug
- (6) Serious TEAEs
- (7) Non-serious TEAEs
- (8) Serious TEAEs Related to Investigational Drug
- (9) Serious TEAEs leading to Discontinuation of Administration of Investigational Drug
- (10) TEAEs Leading to Death

Incidence rates will be calculated as following on each analysis.

[Frequency of Subjects]

• Frequency by Severity

Subjects with one or more adverse events within a level of MedDRA term is counted only once in that level using the most severe incident. The denominator when calculating the incidence of adverse events is the number of subjects of safety analysis set.

· Analyses Other Than the Above

Subjects with one or more adverse events within a level of MedDRA term is counted only once for that MedDRA term. The denominator when calculating the incidence of adverse events is the number of subjects of safety analysis set.

8.1.2. Display of TEAE

Analysis Set: Safety Analysis Set

Analysis Variables: TEAE Category Classification:

Causal relationship with the investigational products [related, unrelated]
Severity [Mild, Moderate, Severe]

Analysis Methods: For the above analysis items, the following analysis is performed for each treatment group. Analysis variables will be coded using the MedDRA dictionary and be summarized into SOC and PT. SOCs will be sorted in alphabetical order, then PTs will be sorted in frequency order.

- 1) All of the TEAEs (by SOC/PT)
- 2) TEAEs Related to Investigational Drug (by SOC/PT)
- 3) TEAEs by Severity (by SOC/PT)
- TEAEs Related to Investigational Drug by Severity (by SOC/PT)
- TEAEs leading to Discontinuation of Administration of Investigational Drug (by SOC/PT)
- 6) Serious TEAEs (by SOC/PT)
- 7) Non-serious TEAEs (by SOC/PT)
- 8) Serious TEAEs Related to Investigational Drug (by SOC/PT)
- Serious TEAEs leading to Discontinuation of Administration of Investigational Drug (by SOC/PT)
- 10) TEAEs Leading to Death (by SOC/PT)

Incidence rates will be calculated as following on each analysis.

[Frequency of Subjects]

• Frequency (by SOC/PT)

Within each summary, subjects with one or more adverse events within a level of SOC term is counted only once in that level. Similarly, subjects with one or more adverse events within a level of PT term is counted only once in that level. The denominator when calculating the incidence of adverse events is the number of subjects of safety analysis set.

• Frequency by Severity (by SOC/PT)

Subjects with one or more adverse events within a level of SOC/PT term is counted only once in that level using the most severe incident. The denominator when calculating the incidence of adverse events is the number of subjects of safety analysis set.

9. LISTING

Following lists will be create for randomized subjects

Demographics

10. CONSIDERATIONS on STATISTICAL ANALYSIS

10.1. Adjustments for Covariates

ANCOVA will be performed on primary and secondary endpoints using treatment group as independent variables, HbA1c (NGSP) at the start of the observation period and SD of 24-hour blood glucose at the start of observation period as covariate. Details are described in 7.1, 7.2 and 7.3.4.

10.2. Handling of Dropouts or Missing Data

For laboratory test, a value below determination limit are treated as zero.

10.3. Criteria for Interim Analysis and Early Discontinuation Interim analysis will not be performed.

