9.1.7 Laboratory tests

Laboratory tests in table 9.a shall be measured at clinical laboratory institutions according to the observation schedule (Appendix A). Regarding tests at fasting, blood sampling shall be conducted after ≥ 10 hours of fasting. The principal investigator and investigator shall evaluate and keep the reported laboratory test results.

Inhibitory rate of DPP-4 activity will be calculated by the sponsor using formula below:

Inhibitory rate of DPP-4 activity (%) = (DPP-4 activity at start of observation period – DPP-4 activity at each visit of treatment period) / DPP-4 activity at start of observation period x 100

Table 9.a Laboratory tests

Serum chemistry	
Fasting blood glucose	Glycoalbumin
Fasting insulin	1,5-AG
Fasting glucagon	
Fasting proinsulin	
FastingGLP-1	
Fasting GIP	
DPP-4 activity	

The principal investigator shall keep laboratory test reference values, including the historical data.

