13.1.3 Efficacy analysis

[Primary endpoints]

Changes in the SD of 24-hour blood glucose values (mg/dL) for each 7-day period between
 Week 3 and Week 4 (between Day 22 and Day 28) of the treatment period, calculated from the value at the start of the observation period

(Analysis method)

- ·For the "full analysis set", summary statistics (number of subjects, mean, SDs, maximum values, minimum values, quartiles [same apply hereafter]) and 95% confidence interval (two sides) of mean shall be calculated for each treatment group at each evaluation point (each day), and illustrating changes in mean and SD in order to evaluate changes in the SD of 24-hour blood glucose values (mg/dL) for each 7-day period between Week 3 and Week 4 (between Day 22 and Day 28) of the treatment period, calculated from the value at the start of the observation period for trelagliptin or alogliptin separately.
- · Preliminary, for the "full analysis set", calculate point estimation and 95% confidence interval (two

sides) in difference of mean in treatment groups (trelagliptin 100 mg group – alogliptin 25 mg group) in order to examine the influence of the once-weekly administration and blood glucose fluctuations due to the difference in the daily administration exploratory.

- · As well, for the "full analysis set," conduct analysis of covariance at each evaluation point with changes in the SD of 24-hour blood glucose values between Week 3 and Week 4 from the value at the start of the observation period as dependent variable, treatment groups as independent variable, HbA1c (NGSP value) at the start of the observation period, changes in the SD of 24-hour blood glucose values at the start of the observation period, and age as covariates, and calculate point estimation and 95% confidence interval (two sides) in difference of adjusted mean for each group.
- · Preliminary, "full analysis set," calculate point estimation and 95% confidence interval (two sides) in difference of adjusted mean in treatment groups (trelagliptin 100 mg group alogliptin 25 mg group)

[Secondary endpoints]

- Changes in AUC over time when specific blood glucose levels (110, 140, 160, or 180 mg/dL) are observed during the 3 hour time period after breakfast, lunch and evening meal*1, 2
- Change in AUC over time during periods when blood glucose 140, 160, or 180 mg/dL (hyperglycemia) is observed*1,2
- Changes in blood glucose 140, 160, or 180 mg/dL (hyperglycemia) over time*1,2

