5. OTHER DATA HANDLING

[Definition of Daytime]

· Time zone from wake-up time to bedtime

[Definition of Nocturnal Period]

• Time zone from bedtime to wake-up time

[Data Handling for Study Drug]

· Duration of Treatment

Duration of Treatment = Date of the Last Dose – Date of the First Dose + 1

[Data Handling for Adverse Event]

- An adverse event is defined as any untoward medical occurrence in a patient or a subject receiving a pharmaceutical product (including the study drug). It does not necessarily have an apparent causal relationship with this pharmaceutical product (including study drug).
- Adverse events, excluding serious adverse events (protocol 10.1.3), shall be non-serious adverse events in the case of an incidence of over 5% in at least one treatment group.

[Data Handling for Laboratory Test Results]

Inhibitory Rate of DPP-4 Activity (%)
 Inhibitory rate of DPP-4 activity (%) = (DPP-4 activity at start of observation period –
 DPP-4 activity at each visit of treatment period) / DPP-4 activity at start of observation period x 100

[Data Handling for Duration of Diabetes (year)]

Duration of Diabetes (year)

Duration of diabetes (year) = (Date of Informed Consent (year/month) – Onset Date of

Diabetes (year/month)) / 12 (rounded off two decimal places)

If only the month of the onset of diabetes is unknown, the month of the onset of diabetes is regarded as "January".

6. SUBJECTS, DEMOGRAPHIC and OTHER BASELINE CHARACTERISTICS

- 6.1. Subject Disposition
- 6.1.1. Study Information

Analysis Set: All subjects who were obtained informed consent

Analysis Variables: The earliest date of informed consent

The latest date of the last date of administration

Version of MedDRA

Version of SAS

Analysis Methods: For the above analysis items, the following analysis is performed.

(1) Show above items.

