AUC over time during periods when blood glucose 140 mg/dL is observed (start of the observation period)

AUC over time during periods when blood glucose 160 mg/dL is observed (Start of the observation period)

AUC over time during periods when blood glucose 180 mg/dL is observed (Start of the observation period)

Cumulative time during periods when blood glucose 140 mg/dL is observed (Start of the observation period)

Cumulative time during periods when blood glucose 160 mg/dL is observed (Start of the observation period)

Cumulative time during periods when blood glucose 180 mg/dL is observed (Start of the observation period)

AUC over time during periods when blood glucose <70 mg/dL is observed (Start of the observation period)

Peak postprandial glucose over time 3 hours after breakfast (Start of the observation period)

Peak postprandial glucose over time 3 hours after lunch (Start of the observation period)

Peak postprandial glucose over time 3 hours after evening meal (Start of the observation period)

Maximum variation of blood glucose over time between before and after breakfast (Start of the observation period)

Maximum variation of blood glucose over time between before and after lunch (Start of the observation period)

Maximum variation of blood glucose over time between before and after evening meal (Start of the observation period)

MAGE (Start of the observation period)

Mean 24-hour blood glucose (Start of the observation period)

Mean daytime blood glucose (Start of the observation period)

Mean nocturnal blood glucose (Start of the observation period)

AUC (Start of the observation period)

AUC over time during periods when blood glucose 110 mg/dL is observed (Start of the observation period)

SD of 24-hour blood glucose (Start of the observation period)

SD of daytime blood glucose (Start of the observation period)

SD of nocturnal blood glucose (Start of the observation period)

Glycoalbumin (Start of the observation period)

1,5-AG (Start of the observation period) [Min<= - <10,
$$10$$
<= - <14, 14 <= - <=Max]

Fasting blood glucose (Start of the observation period)

Fasting insulin (Start of the observation period)

Fasting glucagon (Start of the observation period)

Fasting proinsulin (Start of the observation period)

Fasting GLP-1 (Start of the observation period)

Fasting GIP (Start of the observation period)

DPP-4 Activity (Start of the observation period)

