Analysis Methods: For the above analysis items, the following analysis is performed for each treatment group and all subjects in the analysis set.

(1) Frequency distribution for discrete variables and summary statistics for continuous variables

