7.3. Other Analyses

7.3.1. Clinical Laboratory Test

Analysis Set: Full Analysis Set Analysis Variables: Glycoalbumin

1,5-AG

Fasting blood glucose

Fasting insulin

Fasting glucagon

Fasting proinsulin

Fasting GLP-1

Fasting GIP

DPP-4 Activity

Inhibitory Rate of DPP-4 Activity

Time Point: Start of the observation period, Week 3-4 of the treatment period (Day 1, Day 4-6, Day 9)

Analysis Methods: For the above analysis items, the following analysis is performed

(1) For measurement values and changes from start of the observation period, summary statistics and two-sided 95% CI by time point (each Day) will be calculated by treatment group. The time course will be presented graphically using the mean change and SD.

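### Setting below-limit laboratory values to zero scores such a DPP-4 sample as exactly 100% inhibited, and the number of substituted values is only bracketed, not reported

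*SAP*

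**What the plan says.** The only rule in SAP 10.2 (Handling of Dropouts or Missing Data) is "For laboratory test, a value below determination limit are treated as zero". The revision history in SAP 11 shows that it was added in version 2.0 as a clarification. The same revision added the inhibitory rate.

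SAP 2 and 7.3.1 and Protocol 9.1.7 all treat DPP-4 activity as a laboratory test, so the rule covers it. SAP 5 opens the formula with "Inhibitory rate of DPP-4 activity (%) = (DPP-4 activity at start of observation period", and Protocol 9.1.7 closes the same formula with "activity at each visit of treatment period) / DPP-4 activity at start of observation period x 100".

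The planned output in SAP 7.3.1 is: "For measurement values and changes from start of the observation period, summary statistics and two-sided 95% CI by time point", by treatment group, with a graph of mean and SD. Protocol 13.1.3 defines the term as "summary statistics (number of subjects, mean, SDs, maximum values, minimum values, quartiles [same apply hereafter". Baseline laboratory values, including "DPP-4 Activity (Start of the observation period"), are also summarised under SAP 6.2.1 by "Frequency distribution for discrete variables and summary statistics for continuous variables". SAP 9 begins "Following lists will be create for randomized subjects" and then names only demographics.

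The text provided contains no determination limit, no count or flag of substituted values, no alternative substitution, and no rule for a baseline below the limit.

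**The concern.** Both study drugs are DPP-4 inhibitors, so low on-treatment activity is where a determination limit could come into play. The rule turns a result of the form 'inhibition is more than some figure' into 'inhibition is 100%'. The error has one direction, because true activity cannot be negative.

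If every sample in an arm at a time point were below the limit, the table would show mean 100%, SD 0 and a confidence interval of zero width. That looks exact when the assay has supplied only a bound.

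A baseline set to zero makes the rate a division by zero, and the SAP does not say what happens to that subject.

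**Working it through.** The plan states no figure to reproduce, so the check applies its own formula.

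**Inputs.** From the documents: the zero rule (SAP 10.2), the inhibition formula (SAP 5, Protocol 9.1.7), 15 evaluable subjects per arm (Protocol 13.3), and two-sided 95% intervals (SAP 4). Assumed, because the documents are silent: limit/baseline ratio f of 2%, 5%, 10% or 20%, and k of 15 samples below the limit.

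**One sample.** Let baseline be B, the limit L, and the true visit value x with 0 ≤ x < L.
- True inhibition: 100 × (1 − x/B).
- Under the rule: 100 × (B − 0)/B = 100, whatever B is.
- Overstatement: 100x/B, which lies between 0 and 100f with f = L/B.
- If B is itself set to zero, the rate is undefined.

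**Arm mean.** The overstatement is at most 100 × f × k/15. If baselines differ, f is the average of L/B over the k samples. Ceilings in percentage points:

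| f | k = 1 | k = 4 | k = 8 | k = 12 | k = 15 |
|---|---|---|---|---|---|
| 2% | 0.13 | 0.53 | 1.07 | 1.60 | 2.0 |
| 5% | 0.33 | 1.33 | 2.67 | 4.0 | 5.0 |
| 10% | 0.67 | 2.67 | 5.33 | 8.0 | 10.0 |
| 20% | 1.33 | 5.33 | 10.67 | 16.0 | 20.0 |

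With k = 0 the effect is zero.

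**What the planned table reveals.** With n = 15, no missing values and SAS default quantiles, Q1, median and Q3 are the 4th, 8th and 12th ordered values. If a rate displays as exactly 100 only when substituted:
- only the maximum is 100: 1 to 3 substituted
- Q3 is 100 but the median is not: 4 to 7
- the median is 100 but Q1 is not: 8 to 11
- Q1 is 100: 12 to 15

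**Which statistics two substitutions can bound** (assumed data, limit 10% of baseline, t intervals):
- *(a)* 14 measured rates from 80.0 to 82.6 in steps of 0.2, plus one below the limit. At the limit: mean 81.88, SD 2.39, CI 80.56 to 83.20. At zero: mean 82.55, SD 4.90, CI 79.84 to 85.26. Q1, median and Q3 are 80.6, 81.4 and 82.2 either way.
- *(b)* 7 measured rates from 80.0 to 81.2, plus 8 below the limit. The mean runs from 85.61 (limit) to 90.95 (zero), the median and Q3 from 90 to 100, and Q1 is 80.6 in both.
- *(c)* All 15 below the limit, with true rates evenly spread between 90 and 100. Truth: mean 95.0, SD 2.80, CI 93.45 to 96.55. Zero gives 100 with SD 0, and the limit gives 90 with SD 0. The mean is bounded; the SD and CI are not.

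In 20,000 simulated arms of 15 (1 to 14 below a 10% limit, measured rates uniform on 75 to 90, true censored rates uniform on 90 to 100), the mean, median and quartiles never left the range between the two substitutions. The SD did in about 2.4% of arms and the lower CI limit in about 6%.

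**Other analytes.** For a change from baseline, zero substitution gives an error between 0 and +1 limit if only baseline is below the limit, between −1 limit and 0 if only the visit value is, and between −1 and +1 limit if both are.

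**The case against.** The rule is explicit, reproducible, fixed in the SAP and the same in both arms. DPP-4 activity and its inhibitory rate are among the other endpoints and are described within arm only; SAP 7.3.1 plans no between-arm difference, ANCOVA or test for them. Every cell of the ceiling table rests on an assumed limit, and at 2% of baseline the ceiling is 2 points even with all 15 samples substituted. All of this stands, and it sets the grade.

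Three stronger readings are tempting but not supported.
- A reader might infer that the plan hides the substitution. It does not: a maximum of 100% signals it, the quartiles bracket the number, and the all-substituted case (mean 100%, SD 0) reveals itself. What is missing is the exact count.
- A reader might infer that reported inhibition will be materially wrong. Nothing in the documents shows that any sample will fall below the limit.
- A reader might take the lower CI limit to escape the two substitutions in about 15% of simulated arms. That figure arises only if the limit-substituted result must be the floor and the zero-substituted one the ceiling. It then counts cases lying between the two, such as example (a) with a true value of 95, where 80.20 sits between 79.84 and 80.56. Outside both values the figure is about 6%.

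Suppressing the SD or CI would also go too far, since Protocol 13.1.3 requires summary statistics and a 95% CI at each evaluation point.

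**Conclusion.** The point holds as a minor one. With a measurable baseline, a below-limit visit value is recorded as 100% inhibition when only a lower bound is known. The error in the arm mean is upward only and at most share × (limit/baseline) × 100 points. Its actual size cannot be stated from the documents and may be zero.

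Pre-specification makes the rule reproducible, but it neither removes the direction of the error nor shows how many values it touched. The undefined rate when baseline is below the limit is a genuine gap, though it may never arise. The effect stops at the descriptive laboratory summaries and their baseline values.

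The algebra needs no assumption. The numerical ceilings rest on the assumed ratios and counts, and the bracketing rests on 15 complete values per arm and SAS default quantiles.

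**What to change.** Keep zero as the named primary substitution for all planned statistics, the 95% CI and the graphs, and add to SAP 10.2:

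> The number of laboratory values below the determination limit is shown by treatment group and time point. Where any exist for DPP-4 activity or its inhibitory rate, the mean, median and quartiles are also shown with these values set to the limit; for the inhibitory rate, zero gives the upper bound and the limit the lower bound. The rate is not calculated if the baseline value is below the limit. The SD and 95% CI are footnoted as depending on the substituted value.

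This needs no new data and leaves the statistics required by Protocol 13.1.3 in place. The cost is one SAP paragraph, a few extra table rows and, where substitution occurs, a slightly less favourable inhibition figure beside the primary one.

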10.4. Multicenter Studies

Analyses for consideration of medical institution will not be performed.

10.5. Multiple Comparisons/Multiplicity

It does not adjust multiplicity.

10.6. Examination of Subgroups

Subgroup analysis will not be performed.

11. REVISION HISTORY

Ver.	Date	Author	Revised Content	Reason for Revision
1.0	12 JUL 2016		-	
			[2.TIME WINDOW]	To avoid doble count of evening meal
			Modification on some	
			reference	• To make a distinction between items
			implementation date of	measured three times and items
2.0	24 JUL 2017		CGM	measured twice and to reflect updated
			 Modification on 	protocol
			description of time	
			window of Laboratory	
			Tests	
			[5.OTHER DATA	· To follow specification document of
			HANDLING]	CGM database
			Modification on	
			Definition of	Requirement of Clinical Trial.gov
			"Daytime" and	
			"Nocturnal Period"	To reflect updated Protocol
			Modification on	
			Definition of	Clarification
			Non-seriousAE	
			Add definition of	
			inhibitory rate of	
			DPP-4 activity	
			Add definition of	
			duration of diabetes	
			[6.2.1.Distribution of	Additional items
			Demographics items]	
			· Add items that were	
			not described as	
			Demographics items in	
			secondary evaluation	
			items	

Ver.	Date	Author	Revised Content	Reason for Revision
			[6.3.2. Diet Therapy	· Clarification
			Compliance and	
			6.3.3.Exercise Therapy	
			Compliance]	
			[7.3.1. Clinical	To reflect updated protocol
			Laboratory Test]	
			Add DPP-4activity a	
			nd inhibitory rate of	
			DPP-4 activity	
			• Add Day 4-6 as time	
			point	
			[7.3.5. Proportion of	Clerical corrections
			Frequency for Blood	
			Glucose Obtained from	
			CGM]	
			• Delete the description	
			in the second edition,	
			"Add analysis as	
			necessary".	
			[8.1.1.Brief Summary	Requirement of Clinical Trial.gov
			of Adverse Events and	Remove unnecessary items
			8.1.2.Display of TEAE]	
			 Add analysis of 	
			frequency distribution	
			of non-serious adverse	
			events, deleted analysis	
			of frequency	
			distribution count by	
			onset time point.	
			[9.2. Handling of	Clarification
			Dropout or Missing	
			Value]	
			Add treatment of	
			values below	
			quantitation limit	

Ver.	Date	Author	Revised Content	Reason for Revision
			[6.1.3. Exit Status of	Clerical corrections
			Subjects]	
			• Remove "Exit status	
3.0	28 JUL 2017		from the treatment of	
			study drug" and add	
			"Exit status from the	
			study"	
			[Title page]	· Clerical corrections
4.0	25 JUL 2017		Modification on	Organizational change
			organization name	
			[9. Listing]	Addition of listing
			Add listing of	
			background factor
